### ***6.1.4 Interim Analyses***

A single analysis at the conclusion of the investigation is intended. No interim analyses will be performed. However, in order to monitor patient safety a Sponsor-Independent Data Monitoring Committee (IDMC) was formed and regularly convened according to the requirements of the IDMC Charter to assess the accumulating data.

The safety data provided to the IDMC will be unblinded by a study Independent Statistician to enable identification of treatment group and simplify the medical review process.

IDMC data summaries and listings required for review purposes are given in the IDMC Charter.

The primary analysis is considered to be once all patients have completed Day 90 (or earlier in the event of withdrawal). Once these data become available the evaluation of the efficacy endpoints that relate to the Short Term Follow Up at 28 days and the Long Term Follow Up at Day 90, together with all available safety will reported. Efficacy endpoints associated with later time points (Day 180 and Day 360) will be analysed subsequently and any accumulating safety data re-presented where appropriate.

### ***6.1.5 Blind Data Review***

Prior to the Day 90 database lock and unblinding a blinded review of the entire data up to Day 90 (and any available post Day 90 data) will be performed.

This will serve several purposes. It will enable identification of questionable values, potential outlier patients and potential missing data which may require ratification. It will enable identification of potential sources of variability (see Section 5.9.5) and it will enable assessment of the structure of the table shells. Patient populations will then be assigned by the Sponsor according to the definitions in Section 4 of this SAP.

For evaluation of the suitability of the table shells a 'dummy' randomisation will be used which has a known structure to prevent mistaking for the actual randomisation code.

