## 8 STATISTICAL METHODS

The statistical considerations summarised in this section outline the plan for data analysis of this study.

Before unblinding/database lock, a separate Statistical Analysis Plan (SAP) will be finalised, providing detailed methods for the analyses outlined below. After the clinical parts of the study have been completed, a blinded review of the data will be undertaken according to the SAP. This review will make decisions regarding: the handling of missing data and data for withdrawn patients; the handling of countries recruiting only a small number of patients in the statistical analyses that include country effects; and the definition of the Per-Protocol Set (PPS) at the patient level. Any deviations from the planned analyses will be described and justified in the final integrated study report.

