#### 9.1.1 Database Management and Quality Control

All study-related data generated by site personnel will be captured electronically at each study centre using the e-CRF.

Central laboratory assays (e.g., PD, genetic) will be managed by the central laboratories and results will be transferred for inclusion in the study analysis database.

Once the e-CRF clinical data have been submitted, corrections to the data fields will be captured in an audit trail. The reason for change, the name of the person who performed the change, and the time and date will be logged to provide an audit trail.

The specific procedures to be used for data entry and query resolution using the e-CRF will be provided to study sites in CRF completion instructions. In addition, site personnel will receive training on the e-CRF. Once the source data verification is complete and all queries are closed, Data Management will freeze the e-CRF page.

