#### ***4.1 Protocol Deviations Considered to be Violations***

Subject specific protocol deviations are defined and entered by Investigators, or CRAs, in the eCRF, and are graded as either minor or major.

But Violations are those protocol deviations defined by the Sponsor as being clinically important and may be in whole, or in part, a subset of the eCRF deviations. Any deviation considered by the Sponsor to be a 'violation' will lead to that patient being excluded from the PPS population. Table 1 defines these protocol deviations. To ensure that none of these deviations have been omitted, i.e. not captured by the Investigators and/or CRAs, Data Magik Ltd will programmatically interrogate the clinical study database and extract a listing of the events displayed in Table 1 below.

Furthermore, following the completion of PPD takeover from Gaea of the study management, all deviations in the eCRF database are being transferred and recorded in the PPD CTMS deviation tracker (except for Italian patients, who have not consented themselves). Deviations from these Italian patients will be tracked by the Sponsor using a compatible file to the PPD tracker. Prior to the Day 90 database lock, the deviations will be signed off by the Investigators, exported and sent to DML, and combined with the listing tracker produced from the DML database interrogation

process described above. This combined tracker report showing all deviations will be assessed by the Sponsor, study Medical Monitor and Data Magik Ltd statistical team at the population assignment meeting, and patients to be excluded from the PPS will be identified prior to the Day 90 database lock.

If patients fail to meet one or more of these criteria they will be excluded from the PPS.

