**Table 1: Protocol Deviations Considered to be Violations**

Potential Violations	Detail/Criteria	Reason
Delayed or Incomplete treatment	Failure to treat within first 48 hours of diagnosis or receive less than 3 doses*	IMP needs to be taken within 48 hours of diagnosis and at least 4 doses are deemed necessary for clinical effectiveness
Mis- Dosing	Patient is given incorrect vials leading to 'mixed' treatments	May receive different treatment to the one assigned, or a combination of both treatments
Inclusion criteria	Failed one or more inclusion criterion	Data changed after dosing had commenced
Exclusion criteria	Failed one or more exclusion criteria	Data changed after dosing had commenced
Eligibility	Failed one or more eligibility criteria	Data changed after dosing had commenced
Temperature excursion	IMP must be stored at 2 – 8 °C**	Active ingredient may be affected by temperature excursion.
Other reasons	Any Major Deviation considered by the Sponsor and Medical Monitor that might influence the effectiveness of the active compound	To ensure that the PPS contains only subject data which has not been 'clinically' compromised. Reasons for this decision will be recorded in a comments column on the assignment population spreadsheet during the population assignment meeting.

\*Patients who die during the dosing period will not be excluded from the PPS.

\*\* Individual temperature deviations outside 2-8 may have been accepted and the IMP considered valid for use based on IMP stability data. Those patients who have received an IMP with a temperature excursion, but accepted by the Sponsor, are not classified as Protocol Violations.

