#### **5.6.2 Myxovirus Resistance Protein A (MxA)**

MxA are interferon-induced GTPases and mediate an antiviral response to a broad range of viruses. MxA activity is one of the best markers for IFN beta bioactivity and is often used to monitor the IFN beta treatment in Multiple Sclerosis patients. MxA levels are thus induced by the IFN beta treatment and possibly by the underlying disease. This response is measured on Day 1 Pre-dose and daily thereafter until Day 14 in the ICU.

The Last observation performed whether Day 14 or earlier will be derived.

The change from baseline (Day 1 Pre-dose) will be calculated.

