### ***5.9.5 Strategy For Assessing Sources Of Variability***

Both the Country and Severity of ARDS are considered major sources of variability and potentially influencing factors on the magnitude of the treatment effect. Both are included as strata in the randomisation process. All analyses will include these as factors in statistical models or classification strata for hypothesis tests in order to ensure the precision of estimates obtained.

Recruitment of patients to individual sites within each of the countries is likely to be highly variable. However, although the process of pooling of patients within country should produce a more uniform distribution this will be monitored. In the event of low recruitment in some countries then country pooling strategies may need to be investigated in order to minimise variability. Decisions regarding pooling will take place at the Blind Review.

The impact of patient variability on the Severity of ARDS (Moderate, Severe) will also be explored.

As the adjustment for covariates increases the precision of estimates in proportion to correlation with outcome measure, demographic and other baseline patient data will also be assessed as additional sources of potential variability. Identified variables will be included in the statistical models to evaluate the sensitivity and robustness of the magnitude of the treatment effects determined in the main analyses.

Sources of variability will be assessed at the Blind Data Review prior to database lock at Day 90 and subsequent unblinding. These will include but not limited to the following baseline variables: age, race, sex, Apache score, SOFA score, disease diagnosis, aetiology (including presence/absence of shock), country, PaO2/FiO2 ratio, plateau pressure, tidal volume, PEEP, mode of ventilation, respiratory rate, vasoactive drug use, renal support, patient position, comorbidities from MH coding, season (quarter), study stage, arterial pressure, arterial pH, weight (BMI), renal/liver biochemistry (creatinine, CK, AST, ALT). If other variables are assessed during the blinded review, these will be described in the Day 90 statistical analysis report.

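### The blinded data review covers the whole Day 90 data set with no carve-out for MxA, so those settling discretionary points could guess some patients' arm better than chance

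*SAP*

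**What the plan says.** **Scope of the review.** SAP 6.1.5 provides that "a blinded review of the entire data up to Day 90 (and any available post Day 90 data) will be performed". The review works at patient level: it looks for doubtful values, outlying patients and gaps, searches for sources of variability, and tests the table shells. The only masking device described is a dummy randomisation for the shell check. After that, "Patient populations will then be assigned by the Sponsor according to the definitions in Section 4 of this SAP".

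**Decisions taken at or around it.**
- SAP 4.1: the combined deviation report "will be assessed by the Sponsor, study Medical Monitor and Data Magik Ltd statistical team at the population assignment meeting". The last row of Table 1, Other reasons, allows exclusion from the per-protocol set (PPS) for "Any Major Deviation considered by the Sponsor and Medical Monitor that might influence the effectiveness of the active compound".
- SAP 5.9.5: "Decisions regarding pooling will take place at the Blind Review". The same section has baseline covariates weighed at the review, from a list that is expressly open.
- SAP 5.9.3: the non-safety data of any unblinded patient are looked at in this review before they are included.

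**The marker.** Protocol 6.1.2.5 has MxA sampled pre-dose on D1 and daily from D2 to D14; SAP 5.6.2 ties this to the ICU stay. SAP 5.6.2 ranks MxA among the leading indicators of interferon-beta activity and adds that "MxA levels are thus induced by the IFN beta treatment and possibly by the underlying disease". Under Protocol 9.1.1, central laboratory assays, pharmacodynamic (PD) ones included, are managed by those laboratories and "results will be transferred for inclusion in the study analysis database". SAP 7.6 puts per-patient listings of MxA, CD73, PIM and antibody results in the Day 90 report.

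**The intent.** Protocol 5.4 keeps the overall code closed until patients have been assigned to the analysis sets.

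**The concern.** A pre-unblinding review has value only if the people making the choices do not know the arm. Withholding the code achieves that if nothing else in the data reveals it. Here the reviewed data include, on the plan's own wording, repeated measurements of a protein that the study drug induces. Each patient has a pre-dose value for comparison, and patients with previous interferon are excluded (Protocol 4.2, criterion 9). A rise after D1 is therefore evidence of active treatment, and the same people see the outcomes.

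At stake is whether the trial can show that its discretionary decisions were blind. One of them, country pooling, shapes the primary test. Another, the handling of unblinded patients' data, can affect which data enter it. The other two concern the supporting PPS and the sensitivity analyses.

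**Working it through.** The plan states no figure to reproduce. The check is one of text, followed by one illustration.

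**1. Are MxA results inside the review window?** Sampling ends at D14, well before Day 90. Post-baseline samples run from D2 to D14: 14 − 2 + 1 = 13 at most per patient, fewer if the patient leaves the ICU or dies earlier. SAP 6.1.5 excludes no data domain. Protocol 9.1.1 sends the results to the analysis database but does not say when. That MxA is in hand at the review follows from the stated scope, not from an explicit date.

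**2. Does anything mask it?** The dummy randomisation in SAP 6.1.5 scrambles treatment labels in the shells, so tables produced there show no true arm separation. It leaves each patient's own MxA values unchanged. No section holds PD or antibody results back.

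**3. Which decisions are still open at that point?**

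| Decision | Where | What it reaches | How far it is constrained |
|---|---|---|---|
| Country pooling | SAP 5.9.5; Protocol 8 and 8.2.1.4 | Strata of the primary van Elteren test on the Full Analysis Set (FAS; SAP 6.2.3.2) | Prompted by low recruitment; no numerical threshold, no merging rule |
| Data of unblinded patients | SAP 5.9.3 | Efficacy data, possibly the primary analysis | No criterion given |
| Other reasons row | SAP Table 1 | PPS, supporting only | Must be a major deviation, with the reason recorded |
| Covariates | SAP 5.9.5, 6.2.3.2 | Sensitivity analyses only | Candidate list given but open |

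Before pooling, the primary test has 2 severity levels × 8 countries = 16 strata. With 300 patients that averages 300 / 16 ≈ 19 per stratum, so pooling is a realistic prospect if recruitment is uneven.

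**4. How well could the arm be guessed?** The documents give no MxA distribution by arm, so the separation has to be assumed. Take one MxA summary per patient, normal with equal variance in both arms, means d standard deviations apart, 1:1 allocation, and a guess of active above the midpoint. The share guessed correctly is Φ(d/2):

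| Assumed d | Φ(d/2) |
|---|---|
| 0 | 50% |
| 0.5 | 60% |
| 1 | 69% |
| 1.5 | 77% |
| 2 | 84% |
| 3 | 93% |

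Under this model any d above 0 beats chance. SAP 5.6.2 asserts induction, so d = 0 would contradict the plan's own premise; which other row applies is unknown.

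**5. From guess to bias.** This step cannot be computed. The documents give no basis for how often an arm guess would change a pooling, inclusion or covariate decision, or in which direction.

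**The case against.** The other side has a good deal to say.

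- *The inference is uncertain.* SAP 5.6.2 allows that disease may raise MxA, no discrimination figure is given, sampling stops at ICU discharge, and the transfer date is not stated. This stands and limits the claim to better than chance, for some patients. It does not remove the gap, because the stated scope excludes nothing. CD73 and the antibodies are weaker support: no human antibody incidence is given, and SAP 5.6.1 allows that the ADA assay may not be established.
- *Pooling depends on recruitment counts.* True of what prompts it. Which countries are merged, and below what number, is left open.
- *Unblinded patients' codes are already broken.* Where the reviewers know the arm, holding back MxA adds nothing. But Protocol 5.4 asks for the date, time and reason to be recorded; it does not say that the arm is passed to the people at this review.
- *PPS assignment is mostly mechanical.* It runs on signed-off deviation trackers plus a programmed extract (SAP 4.1). This stands, and leaves the Other reasons row as the exposed part.

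A reader might also infer more than the documents support:

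- *That missing-data handling for the primary analysis is open to influence.* Protocol 8 does say "This review will make decisions regarding: the handling of missing data and data for withdrawn patients", but SAP 5.9.6 plans no imputation, and SAP 5.3.3.1 and 5.4.6 treat patients with missing mortality information as alive.
- *That the PPS is the sole robustness check.* SAP 4 allows an as-treated analysis, and SAP 6.2.3.2 allows covariate sensitivity analyses.
- *That covariate choice alters the primary test.* SAP 6.2.3.2 fixes its strata as severity and country.
- *That selective removal of deaths could shift PPS mortality by a stated amount.* That would presume deliberate one-sided exclusion. The Table 1 footnote keeps patients who die during dosing in the PPS, and mortality is not the primary endpoint.

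**Conclusion.** The point holds as a gap in the plan. As SAP 6.1.5 is written, the people who settle country pooling, the inclusion of unblinded patients' data, the Other reasons exclusions and the sensitivity covariates may first see patient-level values of a treatment-induced marker. Blindness of those decisions could not then be demonstrated. That is weaker than saying that the decisions would be unblinded or biased, which the documents do not show.

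This rests on two readings: that the review's scope means what it says, so that PD results are present, and that MxA induction is real, as SAP 5.6.2 states. The 60% to 93% range is an illustration under assumed separations of 0.5 to 3 standard deviations. It is not an estimate for this trial. No sample size, alpha or endpoint figure is affected. The point is a worthwhile, inexpensive improvement and no ground for rejecting the primary analysis.

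**What to change.** In SAP 6.1.5, redefine the scope of the review as *all data except MxA, CD73, PIM and ADA/NAb results*. Add that:

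1. these results stay with the central laboratory or an independent data manager;
2. they are released for merging only after the analysis populations, country pooling, sensitivity covariates and decisions on unblinded patients' data have been signed off;
3. assay quality checks needed before then are run on scrambled patient identifiers.

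The data-transfer arrangements need a matching sentence that fixes the release point, which Protocol 9.1.1 leaves open.

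The cost is a change of wording and a small delay in cleaning the PD data, which moves to just before or just after lock unless it is done on scrambled identifiers. Nothing changes in the endpoint, the primary test, the sample size or patient procedures.

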### ***6.1.6 Long Term and Extended Follow Up Periods (Day 180, Day 360) Addendum Reports***

All data collected up to and including the first 3 months follow up (Short Term Follow Up (Day 1-28 in ICU), Long Term Follow Up (Day 90) together with the primary analyses will be included in the main clinical study report (CSR).

However, all patients will be followed up for another 3 months (Long term Follow Up (Day 180, i.e. Day 90 – Day 180)) and then a further 6 months (Extended Follow Up (Day 360, i.e. Day 180 – Day 360)). Assessments performed at Day 180 and Day 360 will include: Patient Status (including Mortality at Day 360), Quality of life, Respiratory functioning (FEV-1), Neurological functioning (6MWT), Patient Completion, Unblinding, Additional AEs and Death reporting. All are considered efficacy variables, except any additional AE reports, and as such will involve patients from the FAS population. Medications, deviations and comments data will also be followed up after the Day 90 visit at both Day 180 and Day 360.

Separate or addendums to existing tables and listings will be generated. However, all available data up to and including Day 360 will be presented with the main report at Day 90 and Day 180 addendum report.

Details of the outputs required (including summary tables, analyses and listings) are given in Section 7.4.

### ***6.1.7 Pharmacogenetic Evaluations***

The potential influence of patient genotype on the treatment outcome will be performed and reported separately to the main analysis through a specific pharmacogenetic evaluation. The final genetic analyses are to be decided and those results will be reported separately at Day 360.

## **6.2 Statistical Analyses**

### **6.2.1 Overall Study Patient Group**

Basic information regarding the sample of patients obtained to represent the ARDS population will be summarised. This includes: Disposition, Major Protocol Violations and Deviations, Patient Status and Baseline Characteristic Assessments Prior to Treatment Start, and Randomisation. Details are given in Section 7.2.1

### **6.2.2 Baseline Treatment Group Comparability**

No formal statistical comparisons of the treatment groups at baseline will be performed as this serves only to assess the randomisation procedure. A descriptive clinical evaluation of the representativeness of this population sample will be described in the Clinical Study Report (CSR).

### **6.2.3 Efficacy Assessments - Short Term Follow Up**

Assessments performed during Days 1 to 28 during confinement in the ICU are considered of critical importance.

#### **6.2.3.1 Patient Status Assessments**

All Patient Status assessments performed on Days 1 (Pre-dose) then daily on Days 2 - 28 (Day 28 In or Out of ICU), at Early Termination or Last Day in ICU will be summarised (See Section 7.2.3.1).

#### **6.2.3.2 Primary Efficacy Analysis - Ventilation Free Survival (VFDsurv)**

Ventilation Free Survival (VFDsurv) is a composite measure of Mortality and the Number of days free of Mechanical ventilation (VFD) within 28 days among survivors. The Ventilation Free Days (VFD) count requires two consecutive calendar days of unassisted breathing (UAB) and the precise definition is given in Section 5.9.4.1.

The combination of time to event measure (mortality) with a longitudinal measure (VFD) follows methodology for scoring and analysis proposed by Finkelstein and Schoenfeld (Ref 3).

According to the scoring scheme definition and derivation rules described, higher scores indicate better response with the possible integer scores range from -1 to 28.

VFDsurv scores derived will be numerically summarised (excluding means and standard deviations) according to Treatment group (FP-1201-Iyo/Placebo), Severity of ARDS (Moderate/Severe) and Overall according to the FAS population. Separate supporting summaries by Country will also be included.

A non-parametric analysis will be performed as the data distribution is non normal and negatively skewed. This will involve a generalised Wilcoxon rank sum based stratification test which assigns ranks within strata and compares two treatments within strata (Van Elteren hypothesis test) (Ref 4). The Treatment groups are (FP-1201-lyo/Placebo) with stratification variables Severity of ARDS (Moderate/Severe) and Country (1-8). Statistical significance (p-values) obtained will be displayed with the numerical summaries.

The analysis will primarily use the FAS population but this will be repeated using the PPS group as supporting information.

Summary statistics only will be presented for severity of ARDS subgroups and by country, but will not include non-parametric analysis p-values.

Other baseline characteristic variables potentially contributing to sources of variability may be included in further sensitivity analyses and these will be investigated during the blinded review as described in Section 5.9.5.

